2.18 Correlative Studies

In part 1 of the study and in up to 20 patients enrolled in each of the UPS and LPS cohorts, pre- and post-treatment biopsies (week 0, 8) will be required and biopsies at cycle 12 (week 34) and at progression are optional. T cell infiltration as well as suppressor subpopulations will be compared between pre- and post-treatment biopsies.

Blood for research studies will be collected prior to first study drug administration, at week 8, week 20 and week 32 and flow cytometry analyses will be performed to determine the presence of PD-1 expressing T cells, as well as, the proportion of circulating regulatory T cells (T_{regs}) and myeloid-derived suppressor cells (MDSCs).

3. PATIENT SELECTION

3.1 Eligibility Criteria

Patients must have baseline evaluations performed prior to the first dose of study drug and must meet all inclusion / exclusion criteria. Results of all baseline evaluations, which assure that all inclusion and exclusion criteria have been satisfied must be reviewed by the Principal Investigator or his/her designee prior to enrollment of the patient. In addition, the patient must be thoroughly informed about all aspects of the study, including the study visit schedule and required evaluations and all regulatory requirements for informed consent. The written informed consent must be obtained from the patient prior to enrollment. The following criteria apply to all patients enrolled onto the study unless otherwise specified.

3.2 Inclusion Criteria

- 3.2.1 Age \geq 18 years (Age \geq 12 years for patients with bone sarcomas).
- 3.2.2 Histologically confirmed diagnosis of unresectable, recurrent, and/or metastatic high grade soft-tissue or bone sarcoma of one of the following subtypes: soft

tissue sarcomas (leiomyosarcoma, poorly differentiated/de-differentiated liposarcoma, high grade pleomorphic undifferentiated sarcoma/MFH and synovial sarcoma), and bone sarcomas (Ewing sarcoma, osteosarcoma, and chondrosarcoma [de-differentiated or mesenchymal]).

- 3.2.3 ECOG Performance Status of 0 or 1.
- 3.2.4 At least one site of measurable disease on CT/MRI scans as defined by RECIST 1.1. Baseline imaging must be performed within 30 days of dosing.
- 3.2.5 At least one site of accessible disease for pre- and post-treatment core biopsies for at least 20 patients per arm on the expansion cohorts.
- 3.2.6 Patients may have received 1-3 prior systemic therapies in the metastatic setting.
- 3.2.7 Adequate organ function within 14 days of dosing defined as:
 - 3.2.7.1 Absolute Neutrophil Count (ANC) $\geq 1000/\mu L$
 - 3.2.7.2 Platelets \geq 100,000/µL (transfusion independent)
 - 3.2.7.3 Hemoglobin \ge 9 g/dL or \ge 5.6 mmol/L
 - 3.2.7.4 ALT and AST \leq 2.5 x institutional upper limit of normal (ULN) or \leq 5.0 x institutional ULN if considered due to tumor
 - 3.2.7.5 Alkaline phosphatase \leq 2.5 x institutional ULN unless considered due to tumor
 - 3.2.7.6 Serum bilirubin ≤ 1.5 x institutional ULN. **NOTE**: Patients with elevated bilirubin secondary to Gilbert's disease are eligible to participate in the study
 - 3.2.7.7 Serum creatinine ≤ 1.5 x institutional ULN or 24-hour creatinine clearance ≥ 50 ml/min (calculated creatinine clearance using Cockroft-Gault formula is acceptable)
- 3.2.8 Must be willing to provide and have available archival tissue for PD-L1 testing.
- 3.2.9 Written, voluntary informed consent.
- 3.2.10 Fertile men and women of childbearing potential must agree to use an effective method of birth control from providing signed consent and for 120 days after last study drug administration. Women of childbearing potential include premenopausal women and women within the first 2 years of the onset of menopause. Women of childbearing potential must have a negative pregnancy

test \leq 72 hours prior to Day 1 of study.

Effective methods of birth control include: surgically sterile, barrier device (condom, diaphragm), contraceptive coil, intrauterine device (IUD), and abstinence.

- 3.2.11 Life expectancy of >12 weeks.
- 3.2.12 Patients with central nervous system disease are eligible for enrollment if they have received prior radiotherapy or surgery to sites of CNS metastatic disease and are without evidence of clinical progression for at least 4 weeks prior to screening, have no evidence of new or enlarging brain metastases, and are off steroids for at least 7 days before first dose of pembrolizumab.

3.3 Exclusion Criteria

- 3.3.1 Prior systemic therapy targeting PD-1: PD-L1 axis.
- 3.3.2 Patients who are curable by conventional multidisciplinary management.
- 3.3.3 Patients with severe and/or uncontrolled concurrent medical disease that in the opinion of the investigator could cause unacceptable safety risks or compromise compliance with the protocol.
- 3.3.4 Patients who have received wide field radiotherapy ≤ 4 weeks or limited field radiation for palliation < 2 weeks prior to screening or who have not recovered adequately from side effects of such therapy.
- 3.3.5 Patients who have active infections requiring therapy.
- 3.3.6 Patients that are known to be positive for Human Immunodeficiency Virus (HIV) (HIV 1/2 antibodies), active Hepatitis B (HBsAg reactive), or Hepatitis C (HCV RNA [qualitative] is detected); patients with negative Hepatitis C antibody testing may not need RNA testing.
- 3.3.7 Patients that have a known psychiatric or substance abuse disorder that would interfere with cooperation with the requirements of the trial.
- 3.3.8 Patients who received systemic anti-cancer treatment prior to the first dose of study drug within the following time frames:
 - Patients who have received cyclical chemotherapy within a period of time that is shorter than the cycle length used for that treatment (e.g., 6 weeks for nitrosourea, mitomycin-C) prior to starting study drug.
 - Patients who have received biologic therapy (e.g., antibodies) within a period of time that is $\leq 5 t_{1/2}$ or ≤ 4 weeks (whichever is shorter) prior to starting

study drug.

- Patients who have been treated with a continuous or intermittent small molecule therapeutics within a period of time that is $\leq 5 t_{1/2}$ or ≤ 4 weeks (whichever is shorter) prior to starting study drug.
- Patients who have received any other investigational agents within a period of time that is $\leq 5 t_{1/2}$ or less than the cycle length used for that treatment or ≤ 4 weeks (whichever is shorter) prior to starting study drug.
- Patients who have received wide field radiotherapy (including therapeutic radioisotopes such as strontium 89) ≤ 4 weeks or limited field radiation for palliation ≤ 2 weeks prior to starting study drug.
- Patients who have undergone surgery ≤ 2 weeks prior to starting study drug (minor surgical procedures may be allowed).
- 3.3.9 Patients with active autoimmune disease or a documented history of autoimmune disease or syndrome that requires systemic steroids or immunosuppressive agents. Patients with vitiligo or resolved childhood asthma/atopy would be exception to this rule. Patients that require inhaled steroids or local steroid injections would not be excluded from the study. Patients with hypothyroidism not from autoimmune disease that is stable on hormone replacement will not be excluded from the study.
- 3.3.10 Women who are pregnant or nursing/breastfeeding.
- 3.3.11 Known hypersensitivity to pembrolizumab or another mAb (another PD-1 monoclonal antibody). This is only in the case of pembrolizumab or related mABs hypersensitivity
- 3.3.12 Has a history of (non-infectious) pneumonitis that required steroids or current pneumonitis.
- 3.3.13 Patients with untreated central nervous system disease. Patients with controlled treated CNS lesions who have undergone surgery or stereotactic radiosurgery and stable for 4 weeks are eligible.
- 3.3.14 Inability to comply with protocol required procedures.
- 3.3.15 Patients with medical conditions that require chronic systemic corticosteroid therapy or require any other form of immunosuppressive medication. However, patients using physiologic replacement doses of hydrocortisone, or its equivalent, will be considered eligible for this study: up to 20 mg hydrocortisone (or 5 mg of prednisone) in the morning and 10 mg hydrocortisone (or 2.5 mg prednisone) in the evening.
- 3.3.16 Patients with the risk factors for bowel obstruction or bowel perforation (examples include but not limited to a history of acute diverticulitis, intra-

abdominal abscess, abdominal carcinomatosis).

- 3.3.17 Patients who have received a live vaccine within 30 days prior to the first dose of trial treatment.
- 3.3.18 Patients who have had allogeneic SCT/solid organ transplant

3.4 Inclusion of Women and Minorities

Men, women, children (age ≥ 12 for bone sarcomas only), and members of all ethnic and racial groups are eligible for this trial.

4. REGISTRATION PROCEDURES

4.1 General Guidelines

After obtaining informed consent, only eligible patients will be enrolled in this trial. Eligible patients will be registered by local sites through an electronic database, and will be issued a subject unique identifying number. An investigator is required to prepare and maintain adequate and accurate case histories designed to record all observations and other data pertinent to the investigation on each patient treated with the study drug in the study or registered to the study. SARC may request faxed copies of selected source documents with PHI redacted for verification of records, accuracy of electronic submissions and review of data.

While all study evaluations must be performed by the Investigator, as described in Section 10 (Study Evaluations and Study Calendar), only data related to the primary and secondary endpoints, as well as safety data, will be captured in the eCRFs.

4.2 Registration Process

This study uses a web based data capture system. All patient registration and Case Report Forms (CRFs) will be submitted electronically via a web-based electronic database. All patients must be registered on the study website prior to start of treatment. Data Managers and other authorized users will be provided with a unique user identification number and password to access the site. All study case report forms may be accessed online through the study website. In case there are problems accessing the website, please contact the SARC office directly by [contact] or by [contact].

5. TREATMENT PLAN

5.1 Agent Administration

Pembrolizumab will be administered at 200 mg intravenously every 3 weeks. The pharmacist will prepare pembrolizumab for administration. The Pharmacy Manual that contains specific instructions for pembrolizumab dose calculation, reconstitution,

preparation and administration of the infusion fluid will be provided by Merck. The treatment dosing schedule for this trial is outlined below in Table 1.

| Table 1. Treatment Dosing Schedule | | | | | |
|------------------------------------|--------------|------------------|----------------|---------------------|--------------|
| Drug | Dose/Potency | Dose | Route of | Regimen/Treatment | Use |
| | | Frequency | Administration | Period | |
| Pembrolizumab | 200 mg | every 3 weeks | IV infusion | 30 minutes (-5/+10) | Experimental |

Table 1: Treatment Dosing Schedule

The pembrolizumab dosing interval may be increased due to toxicity as described in Section 6.2. Pre medications will not be administered prior to study drug.

5.2 Time of Drug Administration

Study drug should be administered on Day 1 of each cycle after all procedures/assessments have been completed as detailed on the Study Calendar (Section 10). After the first cycle, trial treatment may be administered \pm 3 days to the scheduled Day 1 of each cycle.

All trial treatments will be administered on an outpatient basis.

Pembrolizumab will be administered as a 30 minute IV infusion (treatment cycle intervals may be increased due to toxicity as described in Section 6.2). Sites should make every effort to target infusion timing to be as close to 30 minutes as possible. However, given the variability of infusion pumps from site to site, a window of -5 minutes and +10 minutes is permitted (i.e., allowed infusion time is between 25 and 40 minutes).

5.3 Trial Blinding/Masking

This is an open-label trial; therefore, the Sponsor, site Investigator and patient will know the treatment to be administered. All enrolled patients will receive pembrolizumab.

5.4 General Concomitant Medication and Supportive Care Guidelines

5.4.1 Concomitant Medications/Vaccinations

Any concomitant medications that the patient is taking that leads to an Adverse Event (AE) grade 1 or greater based on CTCAE v 4.0 will be recorded. This data will be captured on the Adverse Events eCRF.

Also, any concomitant medication abnormality fulfilling the criteria for a Serious Adverse Event (SAE) should be reported as such, in addition to being recorded as an adverse event in the eCRF.

5.4.1.1 Prohibited Concomitant Medications

Patients are prohibited from receiving the following therapies during the Screening and Treatment Phase (including retreatment for post-complete response relapse) of this trial:

- Anti-cancer systemic chemotherapy or biological therapy
- Immunotherapy not specified in this protocol
- Chemotherapy not specified in this protocol
- Investigational agents other than pembrolizumab
- Radiation therapy
 - Note: Radiation therapy to a symptomatic solitary lesion or to the brain may be allowed after consultation with Sponsor.
- Live vaccines within 30 days prior to the first dose of study drug and while on study. Examples of live vaccines include, but are not limited to the following: measles, mumps, rubella, chicken pox, yellow fever, rabies, BCG, and typhoid (oral) vaccine. Seasonal influenza vaccines for injection are generally killed virus vaccines and are allowed; however intranasal influenza vaccines (e.g. Flu-Mist®) are live attenuated vaccines, and are not allowed.
- Glucocorticoids for any purpose other than to treat or prevent any AE, or to modulate symptoms from an event of clinical interest of suspected immunologic etiology. The use of physiologic dose of corticosteroids is allowed.

Patients who require the use of any of the aforementioned treatments for clinical management, per the site Investigator's assessment should be removed from the trial. Patients may receive other medications that the investigator deems to be medically necessary.

The Exclusion Criteria describes other medications which are prohibited in this trial.

There are no prohibited therapies during the Post-Treatment Follow-up Phase.

5.4.2 Rescue Medications & Supportive Care

5.4.2.1 Supportive Care Guidelines

Patients should receive appropriate supportive care measures as deemed necessary by the treating site Investigator including but not limited to the items outlined below:

Pneumonitis:

• For **Grade 2 events**, treat with systemic corticosteroids (1-2 mg/kg/day of prednisone or equivalent).

- For Grade 3-4 events, bronchoscopy should be performed to exclude infectious etiologies before starting immunosuppression. Once infectious etiologies are excluded, immediately treat with intravenous steroids (1-2 mg/kg/day of prednisone or equivalent). If symptoms persist for more than 3-5 days, then begin infliximab 5 mg/kg. When symptoms improve to Grade 1 or less, steroid taper should be started and continued over no less than 4 weeks. Permanently discontinue pembrolizumab.
- When symptoms improve to Grade 1 or less, steroid taper should be started and continued over no less than 4 weeks. Permanently discontinue pembrolizumab.
- Add prophylactic antibiotics for opportunistic infections in the case of prolonged steroid administration.

Diarrhea/Colitis:

Subjects should be carefully monitored for signs and symptoms of enterocolitis (such as diarrhea, abdominal pain, blood or mucus in stool, with or without fever) and of bowel perforation (such as peritoneal signs and ileus).

- All subjects who experience diarrhea/colitis should be advised to drink liberal quantities of clear fluids. If sufficient oral fluid intake is not feasible, fluid and electrolytes should be substituted via IV infusion. For Grade 2 or higher diarrhea, consider GI consultation and endoscopy to confirm or rule out colitis.
- For **Grade 2 diarrhea/colitis**, administer oral corticosteroids (1-2 mg/kg/day prednisone or equivalent).
- For **Grade 3 or 4 diarrhea/colitis,** treat with intravenous steroids (1-2 mg/kg/day prednisone or equivalent) followed by high dose oral steroids. If grade 3-4 diarrhea persists for more than 3-5 days, then begin infliximab 5 mg/kg.
 - For grade 4 diarrhea/colitis, permanently discontinue pembrolizumab.
- When symptoms improve to Grade 1 or less, steroid taper should be started and continued over no less than 4 weeks.

Type 1 diabetes mellitus (if new onset, including diabetic ketoacidosis [DKA]) or ≥ Grade 3 Hyperglycemia, if associated with ketosis (ketonuria) or metabolic acidosis (DKA)

- For **T1DM** or **Grade 3-4** Hyperglycemia
 - Insulin replacement therapy is recommended for Type I diabetes mellitus and for Grade 3-4 hyperglycemia associated with

metabolic acidosis or ketonuria.

• Evaluate patients with serum glucose and a metabolic panel, urine ketones, glycosylated hemoglobin, and C-peptide.

Hypophysitis:

- For **Grade 2** events, treat with corticosteroids (1-2 mg/kg/day prednisone or equivalent). When symptoms improve to Grade 1 or less, steroid taper should be started and continued over no less than 4 weeks. Replacement of appropriate hormones may be required as the steroid dose is tapered.
- For **Grade 3-4** events, treat with an initial dose of IV corticosteroids followed by oral corticosteroids. When symptoms improve to Grade 1 or less, steroid taper should be started and continued over no less than 4 weeks. Replacement of appropriate hormones may be required as the steroid dose is tapered.

Hyperthyroidism or Hypothyroidism:

Thyroid disorders can occur at any time during treatment. Monitor patients for changes in thyroid function (at the start of treatment, periodically during treatment, and as indicated based on clinical evaluation) and for clinical signs and symptoms of thyroid disorders.

- Grade 2 hyperthyroidism events (and Grade 2-4 hypothyroidism):
 - In hyperthyroidism, non-selective beta-blockers (e.g. propranolol) are suggested as initial therapy.
 - In hypothyroidism, thyroid hormone replacement therapy, with levothyroxine or liothyronine, is indicated per standard of care.
- Grade 3-4 hyperthyroidism
 - Treat with an initial dose of IV corticosteroid followed by oral corticosteroids (1-2 mg/kg/day prednisone or equivalent). When symptoms improve to Grade 1 or less, steroid taper should be started and continued over no less than 4 weeks. Replacement of appropriate hormones may be required as the steroid dose is tapered.
 - Permanently discontinue pembrolizumab for **Grade 4** hyperthyroidism.

Hepatic Adverse Events:

- For **Grade 2** events, monitor liver function tests more frequently until returned to baseline values (consider weekly).
 - Treat with IV or oral corticosteroids (0.5-1 mg/kg/day prednisone or equivalent)
- For Grade 3-4 events, treat with intravenous corticosteroids for 24 to

48 hours (1-2 mg/kg/day prednisone or equivalent. If grade 3-4 hepatitis persists for more than 3-5 days, then begin mycophenolate 1 g twice daily. Permanently discontinue pembrolizumab for AST or ALT > 5x ULN or total bilirubin >3x ULN.

- When symptoms improve to Grade 1 or less, a steroid taper should be started and continued over no less than 4 weeks.
- **Renal Failure or Nephritis**:For **Grade 2** events, treat with corticosteroids (1-2 mg/kg/day prednisone or equivalent).
- For **Grade 3-4** events, treat with systemic corticosteroids (1-2 mg/kg/day prednisone or equivalent). Permanently discontinue pembrolizumab.
- When symptoms improve to Grade 1 or less, steroid taper should be started and continued over no less than 4 weeks.
- Management of Infusion Reactions: Signs and symptoms usually develop during or shortly after drug infusion and generally resolve completely within 24 hours of completion of infusion. For Grade 3-4 events, stop infusion and permanently discontinue pembrolizumab.

Table 2 below shows treatment guidelines for subjects who experience an infusion reaction associated with administration of pembrolizumab (MK-3475).

| NCI CTCAE Grade | Treatment | Premedication at subsequent dosing |
|---|---|--|
| Grade 1 Mild reaction; infusion interruption not indicated; intervention not indicated | Increase monitoring of vital signs as medically indicated until the subject is deemed medically stable in the opinion of the investigator. | None |
| Grade 2 Requires infusion interruption but responds promptly to symptomatic treatment (e.g., antihistamines, NSAIDS, narcotics, IV fluids); prophylactic medications indicated for <=24 hrs | Stop Infusion and monitor symptoms. Additional appropriate medical therapy may include but is not limited to: IV fluids Antihistamines NSAIDS Acetaminophen | Subject may be premedicated 1.5h (± 30 minutes) prior to infusion of pembrolizumab (MK- 3475) with: Diphenhydramine 50 mg |
| NCI CTCAE Grade | Treatment | Premedication at subsequent dosing |

Table 2: Infusion Reaction Treatment Guidelines

| | Narcotics Increase monitoring of vital signs as medically indicated until the subject is deemed medically stable in the opinion of the investigator. If symptoms resolve within one hour of stopping drug infusion, the infusion may be restarted at 50% of the original infusion rate (e.g., from 100 mL/hr to 50 mL/hr). Otherwise dosing will be held until symptoms resolve and the subject should be premedicated for the next scheduled dose. Subjects who develop Grade 2 toxicity despite adequate premedication should be permanently discontinued from further trial treatment administration. | po (or equivalent dose of antihistamine). Acetaminophen 500-1000 mg po (or equivalent dose of antipyretic). |
|--|--|---|
| Grades 3 or 4 Grade 3: Prolonged (i.e., not rapidly responsive to symptomatic medication and/or brief interruption of infusion); recurrence of symptoms following initial improvement; hospitalization indicated for other clinical sequelae (e.g., renal impairment, pulmonary infiltrates) Grade 4: Life-threatening; pressor or ventilatory support indicated | Stop Infusion. Additional appropriate medical therapy may include but is not limited to: IV fluids Antihistamines NSAIDS Acetaminophen Narcotics Oxygen Pressors Corticosteroids Epinephrine Increase monitoring of vital signs as medically indicated until the subject is deemed medically stable in the opinion of the investigator. Hospitalization may be indicated. Subject is permanently discontinued from further trial treatment administration. | No subsequent dosing |

Appropriate resuscitation equipment should be available in the room and a physician readily available during the period of drug administration.

- Steven Johnson syndrome (SJS) and Toxic Epidermal Necrolysis (TEN):
 - For signs or symptoms of SJS or TEN, withhold pembrolizumab and refer the patient for specialized care for assessment and treatment.
 - If SJS or TEN is confirmed, permanently discontinue pembrolizumab.
- o Immune-mediated myocarditis management
 - For suspected immune-mediated myocarditis, ensure adequate evaluation to exclude other etiologies, and administer corticosteroids as appropriate.

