6.2 Withholding/Resuming Therapy

Study therapy will be withheld for the following adverse reactions:

a. A drug-related clinically significant toxicity \geq Grade 2, with the exception of the adverse reactions listed under requirement of permanent discontinuation of study therapy.

b. Grade 2 fatigue does not require the withholding of pembrolizumab.

c. When toxicity resolves or improves to \leq grade 1, therapy with pembrolizumab will resume.

d. In case toxicity does not resolve or improve to \leq grade 1 within 12 weeks after last administration of pembrolizumab, study drug discontinuation should be considered after discussion with SARC and overall study PI. If SARC, study PI and Merck are in agreement, patients who still have grade 2 toxicity at 12 weeks may continue on study only if asymptomatic and controlled.

e. Two dosing delays due to toxicity will be permitted. In the event of a third occurrence of a toxicity, which would require dosing delay, study therapy will be discontinued permanently.

f. For signs or symptoms of SJS or TEN, withhold KEYTRUDA® and refer the patient for specialized care for assessment and treatment.

Dose modification and toxicity management for immune-related AEs associated with pembrolizumab

AEs associated with pembrolizumab exposure may represent an immunologic etiology. These immune-related AEs (irAEs) may occur shortly after the first dose or several months after the last dose of pembrolizumab treatment and may affect more than on body system simultaneously. Therefore, early recognition and initiation of treatment is critical to reduce complications. Based on existing clinical trial data, most irAEs were reversible and could be managed with interruptions of pembrolizumab, administration of corticosteroids and/or other supportive care.

For suspected irAEs, ensure adequate evaluation to confirm etiology or exclude other causes. Additional procedures or tests such as bronchoscopy, endoscopy, skin biopsy may be included as part of the evaluation. Based on the severity of irAEs, withhold or permanently discontinue pembrolizumab and administer corticosteroids. Dose modification and toxicity management guidelines for irAEs associated with pembrolizumab are provided in Table 4.

Table 4: Dose Modification and Toxicity Management Guidelines for Immune-related AEs Associated with Pembrolizumab

General instructions:

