- 1. Corticosteroid taper should be initiated upon AE improving to Grade 1 or less and continue to taper over at least 4 weeks.
- 2. For situations where pembrolizumab has been withheld, pembrolizumab can be resumed after AE has been reduced to Grade 1 or 0 and corticosteroid has been tapered. Pembrolizumab should be permanently discontinued if AE does not resolve within 12 weeks of last dose or corticosteroids cannot be reduced to ≤ 10 mg prednisone or equivalent per day within 12 weeks.
- **3.** For severe and life-threatening irAEs, IV corticosteroid should be initiated first followed by oral steroid. Other immunosuppressive treatment should be initiated if irAEs cannot be controlled by corticosteroids.

| Immune-related AEs | Toxicity grade or conditions (CTCAEv4.0) | Action taken to pembrolizumab | irAE management with corticosteroid and/or other therapies | Monitor and follow- up |
|-----------------------|--|----------------------------------|---|---|
| Pneumonitis | Grade 2 Grade 3 or 4, or recurrent Grade 2 | Withhold Permanently discontinue | • Administer corticosteroids (initial dose of 1-2 mg/kg prednisone or equivalent) followed by taper | Monitor participants for signs and symptoms of pneumonitis Evaluate participants with suspected pneumonitis with radiographic imaging and initiate corticosteroid treatment Add prophylactic antibiotics for opportunistic infections |
| Diarrhea / Colitis | Grade 2 or 3 | Withhold | • Administer corticosteroids (initial dose of 1-2 mg/kg prednisone or equivalent) followed by taper | • Monitor participants for signs and symptoms of enterocolitis (ie, diarrhea, |

| Immune-related AEs | Toxicity grade or conditions (CTCAEv4.0) | Action taken to pembrolizumab | irAE management with corticosteroid and/or other therapies | Monitor and follow- up |
|---|---|----------------------------------|---|--|
| | Grade 4 | Permanently discontinue | | abdominal pain, blood or mucus in stool with or without fever) and of bowel perforation (ie, peritoneal signs and ileus). Participants with ≥ Grade 2 diarrhea suspecting colitis should consider GI consultation and performing endoscopy to rule out colitis. Participants with diarrhea/colitis should be advised to drink liberal quantities of clear fluids. If sufficient oral fluid intake is not feasible, fluid and electrolytes should be substituted via IV infusion. |

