| AST / ALT elevation or Increased | Grade 2 | Withhold | Administer corticosteroids (initial dose of 0.5- 1 mg/kg prednisone or equivalent) followed by taper | • Monitor with liver function tests (consider |
| bilirubin | Grade 3 or 4 | Permanently discontinue | • Administer corticosteroids (initial dose of 1-2 mg/kg prednisone or equivalent) followed by taper | weekly or more frequently until liver enzyme value returned to baseline or is stable |
| Type 1 diabetes mellitus (T1DM) or Hyperglycemia | Newly onset T1DM or Grade 3 or 4 hyperglycemia associated with evidence of β-cell failure | Withhold | Initiate insulin replacement therapy for participants with T1DM Administer anti-hyperglycemic in participants with hyperglycemia | • Monitor participants for hyperglycemia or other signs and symptoms of diabetes. |
| Hypophysitis | Grade 2 | Withhold | | • Monitor for signs and symptoms of |

| Immune-related AEs | Toxicity grade or conditions (CTCAEv4.0) | Action taken to pembrolizumab | irAE management with corticosteroid and/or other therapies | Monitor and follow- up |
|-----------------------------|--|--|---|--|
| | Grade 3 or 4 | Withhold or permanently discontinue ¹ | Administer corticosteroids and initiate hormonal replacements as clinically indicated. | hypophysitis (including hypopituitarism and adrenal insufficiency) |
| Hyperthyroidism | Grade 2 | Continue | • Treat with non-selective beta- blockers (eg, propranolol) or thionamides as appropriate | Monitor for signs and symptoms of thyroid |
| | Grade 3 or 4 | Withhold or permanently discontinue ¹ | | disorders. |
| Hypothyroidism | Grade 2-4 | Continue | • Initiate thyroid replacement hormones (eg, levothyroxine or liothyroinine) per standard of care | Monitor for signs and symptoms of thyroid disorders. |
| Nephritis and Renal | Grade 2 | Withhold | Administer corticosteroids (prednisone 1-2 mg/kg or | • Monitor changes of renal function |
| dysfunction | Grade 3 or 4 | Permanently discontinue | equivalent) followed by taper. | |
| Myocarditis | Grade 1 or 2 | Withhold | Based on severity of AE administer corticosteroids | • Ensure adequate evaluation to |
| | Grade 3 or 4 | Permanently discontinue | | confirm etiology and/or exclude other causes |
| All other immune-related | Intolerable/ persistent Grade 2 | Withhold | • Based on type and severity of AE administer corticosteroids | • Ensure adequate evaluation to |

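### For grade 3-4 pneumonitis, Section 5.4.2.1 puts bronchoscopy before steroids, Section 6.2 and Table 4 set no such order, and nothing says which governs

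*Combined protocol and SAP*

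**What the plan says.** Guidance on treating pneumonitis stands in two places in the combined protocol and SAP.

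- **Section 5.4.2.1 (Supportive Care Guidelines), grade 3-4.** "bronchoscopy should be performed to exclude infectious etiologies before starting immunosuppression". The next sentence ties the start of treatment to that result: "Once infectious etiologies are excluded, immediately treat with intravenous steroids". The section opens with a general allowance for judgement: "Patients should receive appropriate supportive care measures as deemed necessary by the treating site Investigator".
- **Section 6.2, text before Table 4, all suspected immune-related events.** The investigator must evaluate the event well enough to establish its cause or rule out others. On the tests to be used it says: "Additional procedures or tests such as bronchoscopy, endoscopy, skin biopsy may be included as part of the evaluation".
- **Section 6.2, Table 4, pneumonitis row, monitoring column.** "Evaluate participants with suspected pneumonitis with radiographic imaging and initiate corticosteroid treatment". The row covers grade 2 and grade 3 or 4, and the instruction is not split by grade.

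Neither section refers to the other on this event, and no statement of precedence appears.

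**The concern.** The two places differ on when steroids start. Under Section 5.4.2.1, steroids for a grade 3-4 event wait for an invasive procedure and its result. Under Table 4 they follow imaging. The event can be life-threatening, so the timing of first-line treatment matters to the patient.

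It also matters to the data. Safety and tolerability are a secondary objective, and the synopsis and Section 13.4.1 say that safety evaluation will put particular weight on immune-related events. About 10 sites are expected (Section 12.1.3). If sites work from different sections, the duration and outcome of these events could partly reflect the section used. The committee that reviews protocol deviations (Section 12.1.2) would also have no single standard against which to judge a site's conduct.

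**Working it through.** The plan gives no figure on this point to reproduce, so the check is a comparison of texts.

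| Element | 5.4.2.1, grade 3-4 pneumonitis | 6.2 text, any suspected immune-related event | Table 4, pneumonitis row |
|---|---|---|---|
| Imaging | Not named | Not named | Named |
| Bronchoscopy | Should be done | Optional, one of three example tests | Not named |
| Ruling out infection or other causes | Comes before steroids | Evaluation of cause required, no order relative to steroids | Not named |
| What leads to steroids | Infection excluded | Severity of the event | Evaluation by imaging |
| Study drug at grade 3-4 | Permanently stopped | Depends on severity | Permanently stopped |

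1. **Where they agree.** Both specific texts stop study drug permanently at grade 3-4. At grade 2, Section 5.4.2.1 gives systemic corticosteroids with no bronchoscopy step, which fits Table 4. The difference is therefore confined to how grade 3-4 events are worked up and when steroids start.

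2. **Bronchoscopy.** Section 5.4.2.1 expects it at grade 3-4. Section 6.2 permits it. Table 4 is silent.

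3. **Order.** Take a patient with grade 3 pneumonitis whose imaging is done and whose bronchoscopy is pending. By Section 5.4.2.1, steroids wait. By Table 4, nothing holds them back. The two texts give different answers at that moment.

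4. **Can both be met?** Yes. Imaging, then bronchoscopy, then steroids is compatible with every line in the table. The texts are not impossible to follow together. A site that reads only Table 4, however, has no reason to choose that order.

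5. **Does another instruction settle it?** Table 4's general instruction 3 says: "For severe and life-threatening irAEs, IV corticosteroid should be initiated first followed by oral steroid". That orders the route of steroid, intravenous before oral. It does not place steroids before or after a diagnostic test.

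6. **Patients concerned.** Section 13.2 gives 86 patients in the initial enrollment and 30 + 30 = 60 in the expansion, so 86 + 60 = 146 in all. The synopsis and Section 2.16 already report response results for 80 evaluable patients of the 86. That group was therefore enrolled before this text, which looks forward mainly to the 60 expansion patients plus any of the 86 still on treatment. The documents do not say how many those are, and they give no pneumonitis rate.

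**The case against.** The strongest reply is that these are guidelines, not rival orders. Section 5.4.2.1 defers to the investigator and Table 4 is titled as guidelines. The Section 6.2 sentence on bronchoscopy is generic: it covers all organs, could not make any one test compulsory, and need not cancel a specific grade 3-4 instruction elsewhere. Section 6.2 also still requires the cause to be established, so it does not waive the search for infection. The Table 4 cell speaks of suspected pneumonitis of any grade and forbids nothing.

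All of that stands, and it limits the point to what sites could do, not what they would do. It does not remove the point. Discretion does not tell a site which of two written sequences is the protocol's, and the duty to evaluate the cause sets no order relative to steroids.

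A reader might also infer that the two sections conflict on steroids for grade 3-4 hyperthyroidism. Section 5.4.2.1 says "Treat with an initial dose of IV corticosteroid followed by oral corticosteroids (1-2 mg/kg/day prednisone or equivalent", while the Table 4 row says "Treat with non-selective beta- blockers (eg, propranolol) or thionamides as appropriate". The documents do not support that inference. In the text as read, the beta-blocker and thionamide entry sits beside grade 2, which agrees with Section 5.4.2.1 for grade 2. The treatment cell for grade 3 or 4 is empty, perhaps because cells are merged in the source. General instruction 3 supplies the same intravenous-then-oral steroid order for severe events.

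**Conclusion.** The point holds for grade 3-4 pneumonitis only. Two sections of one protocol describe different paths to the first steroid dose, and nothing says which prevails, so sites could treat the same event at different times while each follows a written instruction.

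Its size is modest. It concerns mainly the 60 expansion patients and any original patients still on treatment. Applying it to all 146 would overstate its forward reach. No event count can be given. The objective response rate test, its type I error and its power are unaffected. Nor does the safety objective itself single out immune-related events: it names safety and tolerability, and the emphasis comes from the safety-evaluation text.

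The conclusion assumes that no rule of precedence stands in material not available here, such as the Operations Manual. It takes no view on which sequence is clinically right.

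**What to change.** Reconcile Section 5.4.2.1 with Section 6.2 and the Table 4 pneumonitis row so that a single sequence for grade 3-4 pneumonitis appears, covering imaging, bronchoscopy, exclusion of infection and the start of steroids. Alternatively, keep the guidance in one section, cite it from the other, and state which governs. The clinical team must decide the content.

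The cost is protocol wording and a memo to sites. Sample size and the statistical analysis do not change.
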